#### **5.2.4.3 Dose Reductions Due to Adverse Events**

Subjects who experience a Grade 3 or 4 AE (unless the AE is determined to be clearly unrelated to study drug) should have a dose reduction in subsequent treatment cycles to dose level -1 or -2, or as suggested following discussion with the Medical Monitor and/or Sponsor. If the Grade 3 or 4 AE recurs after dose reduction, study treatment must be permanently discontinued. [Table 5-1](#) displays specific toxicities requiring dose reduction and/or discontinuation. Adjustments to these guidelines may occur based on the clinical judgment of the Investigator and with approval of the Medical Monitor.

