**Table 5-1 Toxicities Requiring Dose Reduction**

Toxicities Requiring 1 Dose Level Reduction at First Occurrence	

 
– 2nd occurrence = 2nd dose level reduction
 
– Discontinue after 2 dose level reductions
 
	
Serosal Effusions and Edema	
 
• Grade 2 or higher pericardial effusion
 
• Grade 2 or higher pleural effusion
 
• Grade 2 or higher ascites
 
• Grade 2 or higher peripheral edema
 

Hematology	
 
• Grade 3 thrombocytopenia (platelets <math><50.0\text{--}25.0 \times 10^9/\text{L}</math>)
 
• Grade 4 neutropenia (ANC <math><0.5 \times 10^9/\text{L}</math>) lasting more than 7 days
 
• Grade 3 or higher febrile neutropenia (with ANC <math><1.0 \times 10^9/\text{L}</math>) (concurrent fever <math>\geq 38.3^\circ\text{C}</math>)
 

Laboratory Abnormalities	
 
• Clinically significant Grade 3 or higher non-hematologic laboratory abnormality that does not resolve to Grade 0/1 or baseline within 7 days
 
• Any other Grade 3 or 4 laboratory abnormality considered clinically significant and treatment-related; adjustments to these guidelines may occur based on the clinical judgment of the Investigator and with approval of the Medical Monitor and Sponsor
 
• Grade 2 hypoalbuminemia
 

Other Adverse Events	
 
• Grade 3 photosensitivity reaction (Section 5.5.2)
 
• Grade 3 or Grade 4 nonlaboratory treatment-related toxicity, with the exception of fatigue, asthenia, nausea, or other manageable constitutional symptom
 

Toxicities Requiring 2 Dose Level Reductions at First Occurrence	

 
– Discontinue at second occurrence
 
	

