
 
• Grade 3 serosal effusions (pleural effusions, pericardial effusions, and ascites) and edema
 
• Grade 2 capillary syndrome
 
• Grade 4 thrombocytopenia/ Grade 3 thrombocytopenia with bleeding/ Need for platelet transfusion
 
• Grade 4 febrile neutropenia
 
• Grade 4 (<math>>20.0 \times \text{ULN}</math>) ALT or AST or Grade 3 (<math>>5.0\text{--}20.0 \times \text{ULN}</math>) ALT or AST elevation with concomitant total bilirubin Grade 2 or higher (<math>>1.5 \text{ULN}</math>)
 
• Grade 3 or higher hypoalbuminemia (<math><2 \text{g/dL}</math>)
 
• Grade 2 pneumonitis
 
	

Toxicities Requiring Discontinuation of Investigational Product at First Occurrence

• Grade 4 photosensitivity or skin reaction (Section 5.5.2)

• Drug induced liver injury is confirmed (refer to Section 5.5.3 for definition)

• Life threatening Infusion related reaction or hypersensitivity

• Grade <math>\geq 3</math> pneumonitis

Abbreviations: ALT = alanine aminotransferase; ANC = absolute neutrophil count; AST = aspartate aminotransferase; DILI = drug induced liver injury; INR = International normalized ratio; ULN = upper limit of normal.

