### 13.8 CTCAE v4.03 Grading of Some Relevant AEs

Group	Adverse Event	Grade 1	Grade 2	Grade 3	Grade 4	
Effusions	Ascites	Asymptomatic; clinical or diagnostic observations only; intervention not indicated	Symptomatic; medical intervention indicated	Severe symptoms; invasive intervention indicated	Life-threatening consequences; urgent operative intervention indicated	
	Definition: A disorder characterized by accumulation of serous or hemorrhagic fluid in the peritoneal cavity.					
	Pericardial effusion	–	Asymptomatic effusion size small to moderate	Effusion with physiologic consequences	Life-threatening consequences; urgent intervention indicated	
	Definition: A disorder characterized by fluid collection within the pericardial sac, usually due to inflammation.					
	Pericardial tamponade	–	–	–	Life-threatening consequences; urgent intervention indicated	
Edema	Definition: A disorder characterized by an increase in intrapericardial pressure due to the collection of blood or fluid in the pericardium.					
	Pleural effusion	Asymptomatic; clinical or diagnostic observations only; intervention not indicated	Symptomatic; intervention indicated (e.g., diuretics or limited therapeutic thoracentesis)	Symptomatic with respiratory distress and hypoxia; surgical intervention, including chest tube or pleurodesis indicated	Life-threatening respiratory or hemodynamic compromise; intubation or urgent intervention indicated	
	Definition: A disorder characterized by an increase in amounts of fluid within the pleural cavity. Symptoms include shortness of breath, cough and marked chest discomfort.					
Edema	Edema face	Localized facial edema	Moderate localized facial edema; limiting instrumental ADL	Severe swelling; limiting self-care ADL	–	
	Definition: A disorder characterized by swelling due to excessive fluid accumulation in facial tissues.					
Edema limbs	Edema limbs	5–10% inter-limb discrepancy in volume or circumference at point of greatest visible difference; swelling or obscuration of anatomic architecture on close inspection	>10–30% inter-limb discrepancy in volume or circumference at point of greatest visible difference; readily apparent obscuration of anatomic architecture; obliteration of skin folds; readily apparent deviation from normal anatomic contour; limiting instrumental ADL	>30% inter-limb discrepancy in volume; gross deviation from normal anatomic contour; limiting self-care ADL	–	

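### Section 5.2.4.3 and Table 5-1 give opposite defaults for a recurrent Grade 3/4 toxicity, and Table 5-1 is more lenient for a Grade 4 effusion than for a Grade 3 one

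*Combined protocol and SAP*

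**What the plan says.** Section 5.2.4.3 sets the general rule. A first Grade 3 or 4 AE, unless clearly unrelated to the drug, leads to a reduction of one or two levels, or to whatever is agreed with the Medical Monitor or Sponsor. On recurrence it says: "If the Grade 3 or 4 AE recurs after dose reduction, study treatment must be permanently discontinued". It then refers to Table 5-1 for specific toxicities and allows adjustments with Medical Monitor approval.

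Table 5-1 has three blocks:

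- **One-level block.** For the second event the rule is "occurrence = 2nd dose level reduction", and treatment stops only after two reductions. Rows include "Grade 2 or higher pleural effusion", matching rows for pericardial effusion, ascites and peripheral edema, and "Grade 2 hypoalbuminemia". Two broad laboratory rows and one broad nonlaboratory row cover other Grade 3/4 toxicity.
- **Two-level block.** The recurrence rule is "Discontinue at second occurrence". Rows include "Grade 3 serosal effusions (pleural effusions, pericardial effusions, and ascites) and edema", Grade 2 capillary syndrome, Grade 4 febrile neutropenia and "Grade 3 or higher hypoalbuminemia".
- **Stop-at-first-occurrence block.** It lists no effusion and no capillary syndrome of any grade.

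Appendix 13.8 describes a Grade 4 pleural effusion as "Life-threatening respiratory or hemodynamic compromise; intubation or urgent intervention indicated". Grade 4 is also life-threatening there for pericardial effusion and ascites. Limb edema has no Grade 4.

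**The concern.** A site that has reduced the dose once for a Grade 3/4 toxicity and sees it return finds two instructions in the same section. One is to stop; the other is to reduce again and continue. Two sites could treat the same patient history in opposite ways, each following the protocol.

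For effusions the table is out of order by severity. Serosal effusions are a known and potentially life-threatening toxicity of this drug (Section 5.5.1), and safety is the primary objective. A dose-modification table should not ask for less after a life-threatening effusion than after a Grade 3 one. The planned summary of AEs leading to treatment discontinuation (Section 10.3.7.1) would also partly reflect which recurrence rule each site applied.

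**Working it through.** The plan gives no figure to reproduce. The check sets the rules side by side and counts rows.

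**1. Recurrence after one reduction**

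| Event | Section 5.2.4.3 | Table 5-1 |
|---|---|---|
| Grade 3 thrombocytopenia, no bleeding or transfusion | stop | second reduction |
| Grade 3 photosensitivity | stop | second reduction |
| Grade 4 pleural effusion | stop | second reduction (one-level row only) |
| Grade 3 pleural effusion | stop | second reduction (one-level row) or stop (two-level row) |
| Grade 2 pleural effusion | not covered by the sentence | second reduction |
| Any two-level toxicity of Grade 3/4 | stop | stop |

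The conflict is therefore confined to Grade 3/4 events that fall in the one-level block.

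Rows in that block: 4 effusion/edema + 3 hematology + 3 laboratory + 2 other = 12. Grade 3/4 by definition: 3 hematology + 2 laboratory + 2 other = 7. The four effusion/edema rows run from Grade 2 upward, so they join the conflict when the event is Grade 3 or 4. The one row that never does is Grade 2 hypoalbuminemia.

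**2. Order by severity within Table 5-1**

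| First event | One-level block | Two-level block |
|---|---|---|
| Grade 2 serosal effusion | yes | no |
| Grade 3 serosal effusion | yes | yes |
| Grade 4 serosal effusion | yes | no |
| Grade 2 capillary syndrome | no | yes |
| Grade 3/4 capillary syndrome, treatment-related | yes (nonlaboratory catch-all) | no |

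If the specific Grade 3 row is applied, Grade 3 effusions lose two levels and stop at the second event. Grade 4 effusions lose one level and are reduced again. Capillary syndrome behaves the same way from Grade 2 to Grade 3/4. Grade 4 febrile neutropenia is listed in both blocks, which is an overlap but not an inversion.

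**3. Size on the planned doses (Table 3-1: 0.2, 0.3, 0.4 mg/kg)**

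| Starting dose (mg/kg) | One level down | Two levels down |
|---|---|---|
| 0.4 | 0.3 | 0.2 |
| 0.3 | 0.2 | none planned |
| 0.2 | none planned | none planned |

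From 0.4 mg/kg the table's default dose after a Grade 4 effusion is 0.3 / 0.2 = 1.5 times that after a Grade 3 effusion. The full contrast exists from 1 of the 3 planned levels.

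**The case against.** The strongest defense of the recurrence rules is that a specific table overrides general text. It fails on two counts. The one-level block contains catch-all rows for Grade 3/4 laboratory and nonlaboratory toxicity, so if the table governed, the mandatory sentence in 5.2.4.3 would have little left to apply to. The outcome would also be odd: recurrent Grade 3 fatigue, which the table exempts, would have to stop, while recurrent Grade 3 febrile neutropenia would be redosed. No order of precedence is stated. The Medical Monitor clauses in 5.2.4 and 5.2.4.3 permit departures from a default without saying what the default is.

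Several counterarguments do stand and limit the point:

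- A reader might infer that patients with Grade 4 effusions will in practice be redosed at a 50% higher dose than those with Grade 3. The documents do not support that. Section 5.2.4.3 already allows two levels for any Grade 3/4 AE. Section 5.2.4.1 normally requires resolution first and asks that drained effusions have held steady for two weeks. After a Cycle 1 DLT, 5.2.4.1 restricts further treatment and leaves the dose to the Medical Monitor or Sponsor. A drug-related Grade 3/4 effusion in the first three weeks of Part A is such a DLT. The table's default therefore matters for later events and for Part B.
- A reader might take the 12% rate of Grade 3/4 pleural effusion among 104 earlier subjects (Section 1.4) as an upper bound on how often this arises. It is not one. The affected events also include thrombocytopenia, neutropenia, other effusions and two catch-all categories.
- A reader might see the effusion rows as the one lapse in an otherwise clean table, pointing to hypoalbuminemia, which is split at Grade 3. That split is not clean either: a persistent, clinically significant Grade 3 or higher value also meets a one-level laboratory row, as does persistent Grade 4 ALT/AST. Overlap between blocks is common in this table. What is particular to effusions and capillary syndrome is that the higher grade is missing from the stricter block.
- Whether an uncomplicated second Grade 3 thrombocytopenia should end treatment is a clinical decision for the sponsor. A review can ask that one rule be stated.

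**Conclusion.** Both defects are present in the current text and should be fixed. For Grade 3/4 events in the one-level block, Section 5.2.4.3 and Table 5-1 give incompatible recurrence defaults. Seven of 12 rows are affected by definition, and the four effusion/edema rows when the event is Grade 3 or 4. The row count describes scope and says nothing about risk. Within Table 5-1, the default for serosal effusions and capillary syndrome is more lenient at the worse grade. For effusions this assumes that the specific two-level row is applied at Grade 3.

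The frequency is unknown: the documents give no rate for recurrence after a reduction or for Grade 4 effusions. DLT counts, the MTD and ORR are unaffected. The consequence is inconsistent handling of individual patients and a discontinuation summary that is harder to interpret. That summary is descriptive, so no comparison or error rate is at risk.

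**What to change.** Amend Table 5-1 and Section 5.2.4.3 as follows.

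(a) In the two-level block, write *Grade 3 or higher* for serosal effusions and edema, and *Grade 2 or higher* for capillary syndrome.

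(b) In the one-level block, change the four effusion/edema rows to *Grade 2* and the febrile neutropenia row to *Grade 3*. Add one table note: *If an event meets rows in more than one block, the stricter block applies.* The note also settles the overlap of the persistent Grade 3+ laboratory row with the ALT/AST and hypoalbuminemia rows. It is safer than limiting the catch-all row to toxicities not listed elsewhere, which, unless capillary syndrome is also extended as in (a), could leave Grade 3/4 capillary syndrome in no row.

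(c) State the same recurrence rule in both places. The version consistent with the mandatory wording of 5.2.4.3 is that Grade 2 one-level events get a second reduction at second occurrence and Grade 3/4 events discontinue, with Medical Monitor-approved adjustments kept. If the sponsor prefers staged reduction for particular toxicities, such as uncomplicated Grade 3 thrombocytopenia, list them as exceptions in 5.2.4.3.

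After (a) and (b) the one-level block has 4 + 1 = 5 Grade 2 rows and 7 Grade 3/4 rows. Where no second lower level is planned, the dose stays with the existing Medical Monitor/Sponsor discussion, as it already does for a Grade 3 effusion.

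The cost is a text edit in one amendment, with no new procedures or patients. Some subjects would stop earlier or take a larger reduction than Table 5-1 now prescribes.

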**Table 5-1 Toxicities Requiring Dose Reduction**

Toxicities Requiring 1 Dose Level Reduction at First Occurrence	

 
– 2nd occurrence = 2nd dose level reduction
 
– Discontinue after 2 dose level reductions
 
	
Serosal Effusions and Edema	
 
• Grade 2 or higher pericardial effusion
 
• Grade 2 or higher pleural effusion
 
• Grade 2 or higher ascites
 
• Grade 2 or higher peripheral edema
 

Hematology	
 
• Grade 3 thrombocytopenia (platelets <math><50.0\text{--}25.0 \times 10^9/\text{L}</math>)
 
• Grade 4 neutropenia (ANC <math><0.5 \times 10^9/\text{L}</math>) lasting more than 7 days
 
• Grade 3 or higher febrile neutropenia (with ANC <math><1.0 \times 10^9/\text{L}</math>) (concurrent fever <math>\geq 38.3^\circ\text{C}</math>)
 

Laboratory Abnormalities	
 
• Clinically significant Grade 3 or higher non-hematologic laboratory abnormality that does not resolve to Grade 0/1 or baseline within 7 days
 
• Any other Grade 3 or 4 laboratory abnormality considered clinically significant and treatment-related; adjustments to these guidelines may occur based on the clinical judgment of the Investigator and with approval of the Medical Monitor and Sponsor
 
• Grade 2 hypoalbuminemia
 

Other Adverse Events	
 
• Grade 3 photosensitivity reaction (Section 5.5.2)
 
• Grade 3 or Grade 4 nonlaboratory treatment-related toxicity, with the exception of fatigue, asthenia, nausea, or other manageable constitutional symptom
 

Toxicities Requiring 2 Dose Level Reductions at First Occurrence	

 
– Discontinue at second occurrence
 
	

 
• Grade 3 serosal effusions (pleural effusions, pericardial effusions, and ascites) and edema
 
• Grade 2 capillary syndrome
 
• Grade 4 thrombocytopenia/ Grade 3 thrombocytopenia with bleeding/ Need for platelet transfusion
 
• Grade 4 febrile neutropenia
 
• Grade 4 (<math>>20.0 \times \text{ULN}</math>) ALT or AST or Grade 3 (<math>>5.0\text{--}20.0 \times \text{ULN}</math>) ALT or AST elevation with concomitant total bilirubin Grade 2 or higher (<math>>1.5 \text{ULN}</math>)
 
• Grade 3 or higher hypoalbuminemia (<math><2 \text{g/dL}</math>)
 
• Grade 2 pneumonitis
 
	

Toxicities Requiring Discontinuation of Investigational Product at First Occurrence

• Grade 4 photosensitivity or skin reaction (Section 5.5.2)

• Drug induced liver injury is confirmed (refer to Section 5.5.3 for definition)

• Life threatening Infusion related reaction or hypersensitivity

• Grade <math>\geq 3</math> pneumonitis

Abbreviations: ALT = alanine aminotransferase; ANC = absolute neutrophil count; AST = aspartate aminotransferase; DILI = drug induced liver injury; INR = International normalized ratio; ULN = upper limit of normal.

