### 5.5.2 Skin Reactions

Recommendations for management of photosensitivity reactions are outlined below in [Table 5-2](#).

Photosensitivity was reported in patients treated with Rova-T including severe events.

Photosensitivity reactions may occur hours to days after sun exposure. The median time to onset was 30 days (range 1 to 247 days). Patients should be advised to avoid direct and indirect sun exposure as much as possible during Rova-T treatment and for 30 days after the last dose. If unavoidable, patients should wear protective clothing and sunglasses, and use a broad-spectrum sunscreen and lip balm (SPF 30 or greater). 31 – 90 days after last dose, the patient may resume outdoor activities with appropriate sun protection including broad brimmed hat, protective clothing and sunscreen SPF 30 or higher. Skin reactions should be evaluated promptly and treated with topical or systemic steroids as indicated (refer to [Table 5-2](#)). Rova-T dose should be delayed, reduced or discontinued as necessary (refer to [Table 5-1](#))

All cutaneous reactions which develop during treatment warrant prompt evaluation. Skin toxicity with rovalpituzumab tesirine may consist of photosensitivity but possibly other reactions such as palmar-plantar erythrodysesthesia or erythema multiforme. As such, development of a cutaneous reaction during treatment warrants prompt evaluation by the Investigator or designee:

- If clinically consistent with photosensitivity, the AE should be reported as such (using medically accurate and descriptive AE terminology), and managed as described below in [Table 5-2](#).

- For clinically more severe cases of photosensitivity or if clinically not consistent with photosensitivity, photodocumentation to facilitate later review by the Sponsor or designee may occur.
  - Formal evaluation by a dermatologist, including possible skin biopsy to rule out alternative etiologies, such as erythema multiforme which may warrant discontinuation of study drug, and to facilitate the most appropriate terminology for AE reporting, is recommended.

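### Table 5-2 tells sites to reduce the dose for Grade 4 photosensitivity where Table 5-1 requires stopping; the rules for a recurrent Grade 3 or 4 event also conflict

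*Combined protocol and SAP*

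**What the plan says.** **Grade 4 photosensitivity.** In Table 5-1 the entry "Grade 4 photosensitivity or skin reaction" stands in the block headed "Toxicities Requiring Discontinuation of Investigational Product at First Occurrence". In Table 5-2 the dose-modification column of the Grade 4 row, which describes life-threatening consequences, gives dose reduction, the same action as the Grade 3 row. Section 5.5.2 points to both tables. A reaction that is clinically consistent with photosensitivity is to be reported as such "and managed as described below in" Table 5-2. For dosing, the same section says "Rova-T dose should be delayed, reduced or discontinued as necessary" and refers to Table 5-1.

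**Recurrent Grade 3 or 4 events.** For a first Grade 3 or 4 event not clearly unrelated to the drug, section 5.2.4.3 calls for a reduction to "dose level -1 or -2, or as suggested following discussion with the Medical Monitor and/or Sponsor". It then says: "If the Grade 3 or 4 AE recurs after dose reduction, study treatment must be permanently discontinued". In the one-level block of Table 5-1, the line for a second event reads "occurrence = 2nd dose level reduction", and discontinuation follows only after two reductions. That block contains, among other Grade 3/4 entries, a general row for "Grade 3 or Grade 4 nonlaboratory treatment-related toxicity", with constitutional symptoms excepted.

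**Effusions and edema.** The one-level block lists pericardial effusion, pleural effusion, ascites and peripheral edema at Grade 2 or higher. The two-level block lists serosal effusions and edema at Grade 3 only.

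**The concern.** Safety and tolerability are the primary objective, so sites need one rule for when the drug stops. A clinician treating a severe skin reaction will open Table 5-2, because section 5.5.2 sends photosensitivity management there. For the worst grade, that table prints a dose reduction and so implies continued treatment.

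The toxicity is not remote. Section 1.2 reports drug-related photosensitivity of Grade 3 or above in 7% of subjects in the Phase 2 SCLC study, and section 5.5.2 says that severe events have been seen.

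For recurrent Grade 3 or 4 events, two sites could treat the same course differently, both following the protocol: one stops the drug and the other reduces it again. Dosing and discontinuation records would then differ between sites for reasons unrelated to the subjects.

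**Working it through.** No formula applies; the check is a comparison of the current version 4.0 text.

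| Situation | Text 1 | Text 2 | Does the protocol say which governs? |
|---|---|---|---|
| Grade 4 photosensitivity, first occurrence | Table 5-1: discontinue | Table 5-2, Grade 4 row: reduce dose | Yes, by the dosing pointer in section 5.5.2: Table 5-1 |
| Grade 3/4 event in the one-level block, recurring after one reduction | Section 5.2.4.3: discontinue permanently | Table 5-1, one-level block: second reduction | No |
| Grade 3 effusion or edema, first occurrence | One-level block (Grade 2 or higher) | Two-level block (Grade 3) | No |
| Grade 4 effusion, first occurrence | One-level block (Grade 2 or higher) | Not named in the two-level block | Within Table 5-1, only the one-level block applies |

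**Row 1.** The section 5.5.2 pointer covers delay, reduction and discontinuation alike, and it names Table 5-1. Section 5.2.4.3 also presents Table 5-1 as the list of toxicities that call for reduction or discontinuation. The titles agree with this: Table 5-1 is about required action, Table 5-2 about recommended management. The Table 5-2 cell is therefore the wrong one.

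The next question is whether another rule would catch a site that followed the wrong cell.

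- Serious-event reporting within 24 hours (section 8.1.1.2) and at least weekly assessment of Grade 3 or 4 non-laboratory events (section 5.2.4.2) bring the event to notice. They do not choose the dosing action.
- The pre-dose check in section 5.2.3 asks for resolution to Grade 0 or 1 or to baseline. A Grade 4 reaction that has resolved passes it.
- A Grade 4 skin reaction in the DLT window counts as a DLT unless clearly unrelated to the drug (section 3.1.3). Section 5.2.4.1 then stops treatment unless there is clinical benefit, managed toxicity and approval. That window covers Part A only and lasts 3 weeks, or 3 × 7 = 21 days. Section 5.5.2 gives a median onset of 30 days (range 1 to 247). If onset is counted from the first dose, which the section does not state, 30 > 21, so at least half of photosensitivity events begin after the window closes.

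**Row 2.** The two rules overlap because the one-level block includes Grade 3 thrombocytopenia, Grade 4 neutropenia lasting more than 7 days, febrile neutropenia, Grade 3/4 laboratory abnormalities, Grade 3 photosensitivity and the general nonlaboratory row. There is no conflict for the Grade 2 entries, which section 5.2.4.3 does not reach. There is none for the two-level block either, which stops at the second occurrence, as section 5.2.4.3 does.

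**Rows 3 and 4.** Appendix 13.8 defines a Grade 4 for ascites, pericardial effusion and pleural effusion; its edema terms have none. The Grade 4 gap therefore concerns those three effusions.

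**The case against.** On photosensitivity, the best reply is that the protocol already settles the matter: section 5.5.2 sends dosing decisions to Table 5-1, so a careful site stops the drug. This stands as far as intent goes. A reader might infer that the plan leaves the action for Grade 4 photosensitivity undecided, and the text does not support that. What remains is a wrong cell, in a table that section 5.5.2 tells sites to use and that has its own dosing column.

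On recurrence, it can be argued that Table 5-1 lists specific toxicities and so overrides the general sentence in section 5.2.4.3. Version 4.0 revised Table 5-1 for safety and kept the second-reduction line, which fits that reading. Against it, the block has its own general Grade 3/4 row, so it is not a list of narrow exceptions, and section 5.2.4.3 says that treatment must stop. A reader might infer that the stricter sentence plainly governs and the second reduction is a mistake. The documents do not show this; either rule could be the intended one.

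Sections 5.2.4 and 5.2.4.3 let the investigator depart from the guidelines with Medical Monitor approval. This softens both conflicts for individual subjects but does not say which rule a departure starts from.

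On effusions, a reader might infer that a Grade 4 effusion must be handled more leniently than a Grade 3 one. That goes too far: for any Grade 3 or 4 event, section 5.2.4.3 separately allows a reduction by one level or two and requires a stop on recurrence. The defect lies in the table's grade labels.

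**Conclusion.** The Grade 4 cell of Table 5-2 is wrong as written and should be fixed. It could lead a site that follows that table to re-dose a subject whom Table 5-1 takes off the drug, and the Part A DLT rule limits this only in the first 3 weeks of Cycle 1. The error is one cell. How many subjects it could touch is unknown, because the 7% figure pools Grade 3 with higher grades and comes from an SCLC population.

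The recurrence conflict is also real. It is confined to the Grade 3/4 entries of the one-level block, and it needs a decision by the sponsor. The effusion and edema overlap is minor.

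The first conclusion rests on reading the section 5.5.2 pointer as deciding between the two tables; no sentence says outright that Table 5-1 overrides Table 5-2. A reader might also infer that the response or safety analyses are compromised. Nothing here supports that: no sample size, error rate or planned summary depends on these rules.

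**What to change.** 1. In the Grade 4 row of Table 5-2, replace the instruction to reduce the dose with *Discontinue (see Table 5-1)*. This is one cell, by clarification letter or at the next amendment, with no statistical or enrolment cost.

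2. State which recurrence rule governs, in one of two ways:
   - Limit the second reduction in the one-level block to Grade 2 events, and add that recurrence of a Grade 3 or 4 event after dose reduction means discontinuation under section 5.2.4.3. This is the conservative option. The second reduction would remain for Grade 2 pericardial effusion, pleural effusion, ascites, peripheral edema and hypoalbuminemia.
   - Add to section 5.2.4.3 that, for toxicities in the one-level block, Table 5-1 applies instead.

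   The edit is one line either way, but the choice is clinical. The first option takes some subjects off the drug earlier, for example after recurrent Grade 3 thrombocytopenia. The second allows further dosing after a recurrent Grade 3 or 4 event.

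3. Minor: change the two-level entry for effusions and edema to *Grade 3 or higher*, and cap the one-level effusion and edema entries at Grade 2. These are label changes only.
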